4.1.9 Organ Function Requirements

4.1.9.1 Adequate Bone Marrow Function Defined as:

- a. For patients with solid tumors, including lymphoma, without known bone marrow involvement:
 - Peripheral absolute neutrophil count (ANC) $\geq 1000/\text{mm}^3$
 - Platelet count $\geq 100,000/\text{mm}^3$ (transfusion independent, defined as not receiving platelet transfusions for at least 7 days prior to enrollment)
 - Hemoglobin ≥ 8.0 g/dl, with or without transfusion
- b. Patients with known bone marrow metastatic disease will not be eligible.

4.1.9.2 Adequate Renal Function Defined as:

- Creatinine clearance or radioisotope GFR $\geq 70\text{ml}/\text{min}/1.73 \text{ m}^2$ or
- A serum creatinine based on age/gender as follows:

Age	Maximum Serum Creatinine (mg/dL)	
	Male	Female
1 to < 2 years	0.6	0.6

2 to < 6 years	0.8	0.8
6 to < 10 years	1	1
10 to < 13 years	1.2	1.2
13 to < 16 years	1.5	1.4
≥ 16 years	1.7	1.4

The threshold creatinine values in this Table were derived from the Schwartz formula for estimating GFR³³ utilizing child length and stature data published by the CDC.

4.1.9.3 Adequate Liver Function Defined as:

- Bilirubin (sum of conjugated + unconjugated) ≤ 1.5 x upper limit of normal (ULN) for age
- SGPT (ALT) ≤ 3 × ULN = 135 U/l. For the purpose of this study, the ULN for SGPT is 45 U/l.
- Serum albumin ≥ 2 g/dl.

4.1.10 Informed Consent: All patients and/or their parents or legally authorized representatives must sign a written informed consent. Assent, when appropriate, will be obtained according to institutional guidelines.

4.2 **Exclusion Criteria**

4.2.1 Pregnancy or Breast-Feeding:

Pregnant or breast-feeding women will not be entered on this study due to risks of fetal and teratogenic adverse events as seen in animal studies. Pregnancy tests must be obtained in girls who are post-menarchal. Males or females of reproductive potential may not participate unless they have agreed to use an effective contraceptive method both during and for 3 months after participation in this study. Abstinence is an acceptable method of contraception. Those who become pregnant while on treatment with entinostat must discontinue immediately and consult their treating physician.

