5.5.1 Non-Hematological Dose-Limiting Toxicity

5.5.1.1 Any Grade 3 or greater non-hematological toxicity attributable to the investigational drug with the specific exclusion of:

- Grade 3 nausea and vomiting of less < 3 days duration
- Grade 3 liver enzyme elevation, including ALT/AST/GGT that returns to levels that meet initial eligibility criteria or baseline within 7 days. See [Appendix III](#) for values that represent thresholds between CTCAE grades. Note: For the purposes of this study the ULN for ALT is defined as 45 U/L.
- Grade 3 or 4 fever < 5 days duration.
- Grade 3 infection < 5 days duration.
- Grade 3 hypophosphatemia, hypokalemia, hypocalcemia or hypomagnesemia responsive to supplementation.
- Any Grade 2 non-hematological toxicity that persists for ≥ 7 days and is considered sufficiently medically significant or sufficiently intolerable by patients that it requires treatment interruption.
- Note: Allergic reactions that necessitate discontinuation of study drug will not be considered a dose-limiting toxicity.

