8.0 EVALUATIONS/MATERIAL AND DATA TO BE ACCESSIONED

8.1 Required Clinical, Laboratory and Disease Evaluation

All clinical and laboratory studies to determine eligibility must be performed within 7 days prior to enrollment unless otherwise indicated. Laboratory values used to assess eligibility (see [Section 4.0](#)) must be no older than seven (7) days at the start of therapy. Laboratory tests need **not** be repeated if therapy starts **within** seven (7) days of obtaining labs to assess eligibility. If a post-enrollment lab value is outside the limits of eligibility, or laboratory values are older than 7 days, then the following laboratory evaluations must be re-checked within 48 hours prior to initiating therapy: CBC with differential, bilirubin, ALT (SGPT) and serum creatinine. If the recheck is outside the limits of eligibility, the patient may not receive protocol therapy and will be considered off protocol therapy. Imaging studies must be obtained within 14 days prior to start of protocol therapy (repeat the tumor imaging if necessary).

STUDIES TO BE OBTAINED	Pre-Study	During Cycle 1	Prior to Subsequent Cycles[^]
History	X	Weekly	X
Physical Exam with vital signs	X	Weekly	X
Height, weight, BSA	X		X
Performance Status	X		
CBC, differential, platelets	X	Twice Weekly	Weekly ³
Pharmacokinetics ¹	X	X	X
Urinalysis	X		
Electrolytes including Ca ²⁺ , PO ₄ ³⁻ , Mg ²⁺ ; glucose	X	Weekly	X
Creatinine, ALT, bilirubin	X	Weekly	X
Albumin	X		X
Tumor Disease Evaluation	X	End of Cycle 1	Every other cycle x 2 then q 3 cycles ⁴
Pharmacodynamics Studies (H3 and H4 Histone Acetylation in PBMCs) ⁶	X	X ⁷	
Pregnancy Test ²	X		
Patient Diary ⁵		Weekly	X

[^] Studies may be obtained within 72 hours prior to the start of the subsequent cycle.

¹ See [Section 8.3](#) for timing of PK studies.

² Women of childbearing potential require a negative pregnancy test prior to starting treatment; sexually active patients must use an acceptable method of birth control. Abstinence is an acceptable method of birth control. Patients of reproductive potential must use secure methods of contraception during treatment and for 3 additional months after the end of treatment. Those who become pregnant while on treatment with entinostat must discontinue immediately and consult their treating physician.

³ If patients develop Grade 4 neutropenia or Grade 4 thrombocytopenia then CBCs should be checked every 3 to 4 days until recovery to Grade 3.

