APPENDIX III: TOXICITY-SPECIFIC GRADING

Bilirubin

Grade 1:	≤ 1.5 x ULN
Grade 2:	> 1.5- 3.0 x ULN
Grade 3:	> 3.0-10.0 x ULN
Grade 4:	> 10.0 x ULN

ALT: For the purpose of this study, the ULN for SGPT is 45 U/L regardless of baseline.

Grade 1:	≤ 135
Grade 2:	136- 225
Grade 3:	226- 900
Grade 4:	> 900

AST: For the purpose of this study, the ULN for SGPT is 50 U/L regardless of baseline.

Grade 1:	≤ 150
Grade 2:	151-250
Grade 3:	251-1000
Grade 4:	> 1000

GGT:

Grade 1:	> ULN- 2.5 x ULN
Grade 2:	> 2.5- 5.0 x ULN
Grade 3:	> 5.0-20.0 x ULN
Grade 4:	> 20.0 x ULN

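### AST and GGT (but not ALT) are named in the liver-enzyme DLT text and graded in Appendix III, yet have no scheduled test, no eligibility limit and no protocol-required baseline

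*Combined protocol and SAP*

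**What the plan says.** Section 5.5.1.1 opens with a general rule: "Any Grade 3 or greater non-hematological toxicity attributable to the investigational drug with the specific exclusion of" a list of exceptions. One exception is a "Grade 3 liver enzyme elevation, including ALT/AST/GGT that returns to levels that meet initial eligibility criteria or baseline within 7 days". Section 5.5 makes Cycle 1 the DLT observation period.

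Appendix III gives grade cut-offs for ALT, AST and GGT. The AST block is mislabelled: "AST: For the purpose of this study, the ULN for SGPT is 50 U/L regardless of baseline". GGT is graded in multiples of a ULN that the study does not fix.

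The required-evaluations table in section 8.1 has one liver-enzyme row, "Creatinine, ALT, bilirubin", done pre-study, weekly in Cycle 1 and before later cycles. Neither the table nor its footnotes mention AST or GGT. The pre-treatment recheck in sections 4.0 and 8.1 covers "CBC with differential, bilirubin, ALT (SGPT) and serum creatinine". Among the enzymes, section 4.1.9.3 limits only ALT: "SGPT (ALT) ≤ 3 × ULN = 135 U/l".

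Section 11.2.1 makes DLT evaluability depend on the appropriate toxicity monitoring having been done, without listing the tests. Under section 11.3, two or more DLTs in a cohort of up to six mean that the MTD has been exceeded.

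**The concern.** The DLT text and the grading appendix assume values that the schedule does not produce. This has two consequences, both confined to AST and GGT.

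First, a patient followed exactly to section 8.1 can be counted as free of DLT with neither enzyme ever measured. A patient with the same course at a site whose routine panel includes AST or GGT could be counted as having a DLT. Ascertainment of a named analyte then varies by site.

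Second, the exception turns on return to the eligibility level or to baseline. For AST and GGT there is no eligibility level, and no baseline is required. Where a site draws one of them only after treatment starts, the exception has nothing to refer to. Section 6.2.1 has the same gap, because resumption after a non-hematological DLT is also judged against eligibility parameters or baseline.

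The decision rule is coarse. With two events in up to six patients as the threshold, one event counted at one site and missed at another can change the escalation decision.

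**Working it through.** The plan has no figure of its own to reproduce here. The check is a side-by-side reading, followed by an illustration.

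**What the protocol supplies for each enzyme**

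| | ALT | AST | GGT |
|---|---|---|---|
| Covered by the exception in 5.5.1.1 | yes | yes | yes |
| Grade cut-offs in Appendix III | yes | yes | yes |
| Study-fixed ULN | 45 U/L | 50 U/L (line labelled SGPT) | none |
| Eligibility limit in 4.1.9.3 | 135 U/L | none | none |
| Pre-study test in 8.1 | yes | no | no |
| Weekly test in Cycle 1 in 8.1 | yes | no | no |

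The Appendix III cut-offs are consistent with their ULNs. For ALT, 45 × 3, 5 and 20 gives 135, 225 and 900. For AST, 50 × 3, 5 and 20 gives 150, 250 and 1000. An AST value can therefore be graded if it is measured. The cut-offs set severity; they supply neither an eligibility level nor a baseline.

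**Illustration of the effect on the decision rule**

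Assumptions, none of them in the documents:
- q = 2% to 5% of patients have an attributable Grade 3 AST or GGT elevation and no other DLT.
- 15% of patients have some other DLT.
- The two occur independently, and the cohort is filled to six.

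Chance of at least one AST-only or GGT-only event in six, 1 − (1 − q)^6:
- q = 0.02: 1 − 0.98^6 = 0.114
- q = 0.05: 1 − 0.95^6 = 0.265

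Chance of two or more DLTs in six, 1 − (1 − p)^6 − 6p(1 − p)^5:
- Tests never drawn, p = 0.15: 1 − 0.377 − 0.399 = 0.224
- Drawn and all counted, q = 0.02: p = 1 − 0.85 × 0.98 = 0.167, giving 0.264
- Drawn and all counted, q = 0.05: p = 1 − 0.85 × 0.95 = 0.1925, giving 0.326

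The contrast is between 22% and 26% to 33%. The upper figures are ceilings, because they assume that no event is removed by the 7-day exception.

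**A second set of assumptions.** Suppose instead that 10% of all DLTs appear only as AST or GGT and go unmeasured. The chance of two or more counted DLTs in six then falls:
- from 0.345 to 0.296 at a true DLT rate of 20%;
- from 0.642 to 0.573 at 33%;
- from 0.767 to 0.699 at 40%.

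The rolling six design can escalate after three to five DLT-free patients, so these full-cohort figures simplify the actual rule.

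**The case against.** **The rule is a catch-all.** AST and GGT appear inside an exception, not in a list of required DLT endpoints. The same general rule would capture Grade 3 lipase, amylase, CPK or INR, all mentioned in section 9.1.8 and none scheduled. Following the liver by ALT is a defensible choice. This stands in part: it would be too strong to say that the DLT definition relies on AST and GGT. But these two differ from the other unscheduled analytes. The DLT section names them, gives them a recovery test, and relies on study-specific cut-offs for them.

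**Such events may be rare or not attributable.** A DLT must be at least possibly related to treatment. Section 9.1.8 (n = 221 in the table heading) lists AST and GGT increases among events with insufficient evidence of causation. The adult single-agent DLTs named in section 2.3.1 include no liver-enzyme event. This stands as a limit on size. It does not explain the gap, because ALT is in the same list and is fully scheduled.

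**Central review limits inconsistency.** Suspected DLTs go to the Study Chair within 24 hours (section 5.4), and evaluations are reviewed on a weekly call (section 14.4.2). This helps with values that have been measured. It cannot recover a test that was never drawn.

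**Stronger readings.** A reader might infer that liver-enzyme DLTs in general go unascertained, or that the 7-day test cannot be applied at all. ALT contradicts both: it has a fixed ULN, an eligibility limit, a pre-study value and weekly Cycle 1 tests. A reader might also infer that an AST or GGT event can never meet the exception. The text allows baseline as an alternative, so a site with a pre-treatment value can use it.

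**Conclusion.** The point holds for AST and GGT only. The DLT section and Appendix III refer to analytes that section 8.1 does not schedule, that section 4.1.9.3 does not limit, and for which no baseline is required. Detection of an AST-only or GGT-only Grade 3 event in Cycle 1 depends on local practice. The recovery test has no protocol-required reference unless the site happens to hold one.

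The inconsistency can be read directly from the documents. Its size cannot. The figures of 22% against at most 26% to 33% rest on assumed rates of 2% to 5% and 15%, and on counting every event. They show that a small ascertainment difference can move a two-in-six rule by roughly 4 to 10 percentage points. They do not show that the MTD from this trial would be wrong, and the safety information in section 9.1.8 gives no reason to expect such events to be common.

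**What to change.** Add AST and GGT to the existing creatinine, ALT and bilirubin row of section 8.1, at the same times: pre-study, weekly in Cycle 1 and before subsequent cycles. Every patient then has a baseline for both enzymes and the same chance of detection. The cost is amendment wording and two extra analytes on a chemistry sample already drawn, with no added visit. Uniform measurement may also bring to light events that would otherwise have gone unseen.

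The sponsor should reconcile sections 4.1.9.3, 5.5.1.1, 6.2.1 and 8.1 with Appendix III on which enzymes decide DLT status and what level each must return to. A non-hematological DLT triggers a treatment hold under section 6.2.1, so that choice is a clinical rule and is left to the sponsor here.

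In the same amendment, correct the SGPT label in the AST block of Appendix III and state which ULN applies to GGT.

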5.5.2 Hematological dose limiting toxicity

5.5.2.1 Hematological dose limiting toxicity is defined as:

- Grade 4 thrombocytopenia (platelet count $< 25,000/\text{mm}^3$) or Grade 4 neutropenia (see [Section 6.1](#)), not due to malignant infiltration.
- Grade 3 thrombocytopenia with clinically significant bleeding, petechiae, or purpura or that persists for ≥ 7 days or that requires platelet transfusion on ≥ 2 separate days within a 7-day period.

5.5.2.2 Note: Grade 3 or 4 febrile neutropenia will not be considered a dose-limiting toxicity.

6.0 DOSE MODIFICATIONS FOR ADVERSE EVENTS

The Study Chair must be notified of any dosage modification or use of myeloid growth factor.

6.1 Dose Modifications for Hematological Toxicity

- 6.1.1 If a patient experiences Grade 4 neutropenia or thrombocytopenia, the treatment will be held. Counts should be checked every 3-4 days for thrombocytopenia or neutropenia during this time. If the toxicity resolves to meet eligibility parameters within 14 days of drug discontinuation, the patient may resume treatment at the next lower dose level. For patients enrolled at Dose Level -1 (see [Section 5.3.1](#)), the dose should be reduced to $1.6 \text{ mg}/\text{m}^2$. Doses reduced for toxicity will not be re-escalated, even if there is minimal or no toxicity with the reduced dose.
- 6.1.2 If toxicity does not resolve to meet eligibility parameters within 14 days of drug discontinuation, the patient must be removed from protocol therapy.
- 6.1.3 If hematological dose-limiting toxicity recurs in a patient who has resumed treatment at the reduced dose, the patient must be removed from protocol therapy.

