5.2 Criteria for Starting Subsequent Cycles

A cycle may be repeated every 28 days if the patient has at least stable disease and has again met laboratory parameters as defined in the eligibility section, [Section 4.0. Section 4.0](#)

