6.2 Dose Modifications for Non-Hematological Toxicity

- 6.2.1 If a patient experiences non-hematological dose-limiting toxicity as defined in [Section 5.5.1](#), the treatment will be held. When the toxicity resolves to meet eligibility parameters or baseline within 14 days of drug discontinuation, the patient may resume treatment at the next lower dose level. For patients enrolled at Dose Level -1 (see [Section 5.3.1](#)), the dose should be reduced to $1.6 \text{ mg}/\text{m}^2$. Doses reduced for toxicity will not be re-escalated, even if there is minimal or no toxicity with the reduced dose.
- 6.2.2 If toxicity does not resolve to meet eligibility or baseline parameters within 14 days of drug discontinuation, the patient must be removed from protocol therapy.
- 6.2.3 If the same dose-limiting toxicity recurs in a patient who has resumed treatment at the reduced dose level, the patient must be removed from protocol therapy.

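### Section 6.1.1 orders a hold and one-level reduction only for Grade 4 counts, leaving most Grade 3 thrombocytopenia DLTs with no mandatory hold or reduction

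*Combined protocol and SAP*

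**What the plan says.** Section 5.5.2.1 defines hematological DLT in two bullets. The first is Grade 4 thrombocytopenia or neutropenia. The second is "Grade 3 thrombocytopenia with clinically significant bleeding, petechiae, or purpura or that persists for" at least 7 days, or that needs platelet transfusion on at least 2 separate days within a 7-day period.

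Section 6.1.1 on management reads "If a patient experiences Grade 4 neutropenia or thrombocytopenia, the treatment will be held". If counts recover to eligibility values within 14 days, treatment may resume one level lower. Section 6.1.2 adds: "If toxicity does not resolve to meet eligibility parameters within 14 days of drug discontinuation, the patient must be removed from protocol therapy". Section 6.1.3 orders removal under this condition: "If hematological dose-limiting toxicity recurs in a patient who has resumed treatment at the reduced dose".

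The non-hematological rule is built differently. Section 6.2.1 opens "If a patient experiences non-hematological dose-limiting toxicity as defined in" Section 5.5.1, so its hold and reduction follow the whole DLT definition. That definition begins "Any Grade 3 or greater non-hematological toxicity attributable to the investigational drug with the specific exclusion of" a list of exceptions.

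At a cycle boundary, Section 5.2 allows another cycle if the patient has at least stable disease and "has again met laboratory parameters as defined in the eligibility section". For platelets this means at least 100,000/mm3 and "transfusion independent, defined as not receiving platelet transfusions for at least 7 days prior to enrollment" (Section 4.1.9.1).

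**The concern.** The protocol declares a set of events dose-limiting, then attaches its mandatory response to only part of that set. For the rest, a site that follows Section 6 to the letter has no instruction to stop the next weekly dose and none to lower the dose later. Sites may therefore manage the same DLT differently. A child may also be re-exposed, at the dose that produced the toxicity, while still thrombocytopenic. Section 7.4 bars growth factors that support platelets, so withholding or lowering the drug is one of the main responses left. This is a question of patient safety and internal consistency, not of inference.

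**Working it through.** The plan states no figure on this point, so there is none to reproduce. The check is a mapping of rules, followed by two bounds.

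**1. Each hematological DLT against the mandatory rules**

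| Event under 5.5.2.1 | Mandatory hold and reduction |
|---|---|
| Grade 4 platelets or neutrophils | Yes, 6.1.1 |
| Grade 3 platelets with a bleed that is itself an attributable Grade 3 or higher non-hematological event | Yes, 6.2.1 through 5.5.1.1 |
| Grade 3 platelets with petechiae, purpura or bleeding below Grade 3 | None |
| Grade 3 platelets for 7 days or more | None |
| Grade 3 platelets with transfusion on 2 or more days within 7 | None |

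Other provisions do not fill the last three rows:
- Section 5.2 acts only at the start of a cycle and requires no reduction.
- Section 6.1.2 is not limited to Grade 4 and could apply after a discretionary hold, but nothing obliges anyone to start that hold.
- Section 10.1(b) and the design schema refer to toxicity that requires removal, which leads back to Section 6.
- Section 5.5.1.1 also lists a Grade 2 item among its exclusions. Even if read as a DLT, it covers only non-hematological toxicity that lasts 7 days and already requires interruption.

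**2. Doses that may still be given in Cycle 1**

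Inputs: doses on Days 1, 8, 15 and 22 (Section 5.1). Assumptions: entry platelets are at least 100,000/mm3, so Grade 3 onset is Day 2 at the earliest; a DLT met on a dosing day is counted as after that day's dose.

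- Petechiae, purpura or lower-grade bleeding (DLT met on the onset day): onset Days 2-7 leave 3 doses, Days 8-14 leave 2, Days 15-21 leave 1, Day 22 or later 0.
- Transfusion (DLT met on the second transfusion day, onset + 1 at the earliest): onset Days 2-6 leave 3, Days 7-13 leave 2, Days 14-20 leave 1.
- Persistence (DLT met at onset + 7): onset Days 2-7 leave 2, Days 8-14 leave 1, Day 15 or later 0.

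**3. Reduction forgone in the next cycle**

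The steps not taken are 4 to 3, 3 to 2.3, or 2.3 to 1.6 mg/m2. The unreduced dose is then 4/3 = 1.33, 3/2.3 = 1.30 or 2.3/1.6 = 1.44 times the reduced one. In Appendix IV tablets the difference is 1 or 2 mg a week in nearly every BSA band. For example, at 1.17-1.37 m2 on Level 2 it is 5 against 4 mg, and at 1.88-2.12 m2 it is 8 against 6 mg. It reaches 3 mg only at 2.13-2.16 m2 on Level 2 (9 against 6 mg).

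These figures bound what the text permits. They are not expected harm.

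**The case against.** The best case for the plan is that Grade 4 was chosen as the management threshold, with a wider DLT definition serving escalation only. Section 5.5.2.1 cross-refers to Section 6.1 only in its Grade 4 bullet. Footnote 3 of Section 8.1 starts extra blood counts at Grade 4 and ends them on recovery to Grade 3. Section 6.1.3 can be read to fit: after a Grade 4 hold and reduction, any further hematological DLT means removal. This reading is possible. Against it, Section 6.1.3 speaks of recurrence of the whole DLT category at a reduced dose, and Section 6.2.1 uses the full definition. A reader might infer a proven drafting error; the text suggests one but does not prove it.

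A reader might also compare redosing at counts down to 25,000/mm3 (the Grade 4 limit) with the 100,000/mm3 needed after Grade 4, and call the gap fourfold. That does not measure this omission. Nothing in Section 6.1 stops within-cycle dosing at any Grade 3 count, including a brief, symptom-free one that is not a DLT.

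The safeguards are real. Cycle 1 counts are twice weekly (Section 8.1), DLTs go to the Study Chair within 24 hours (Section 5.4), leadership reviews weekly (Section 14.4.2), and the physician may stop treatment (Section 10.1(e)). They make continued dosing less likely, but all leave the decision to judgment.

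Likelihood is open. The adult phase 1 DLTs named in Section 2.3.1 include no platelet event. Section 9.1.8 lists decreased platelet count as likely (>20%), without grade, and the adult doses and schedules differ.

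**Conclusion.** The gap holds on the text and should be closed, whichever threshold was intended, because the plan states no rule for these three kinds of DLT. Its size is at most 3 further Cycle 1 doses at the unchanged level (2 under persistence), on the day-counting assumptions above, followed by a next cycle without the one-level reduction. Section 6.1 is not confined to Cycle 1, so the same silence applies later.

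A reader might infer that the MTD is at risk. The documents do not support that. These events still count as DLTs under Section 5.5.2, a patient with a DLT is evaluable after a single dose (Section 11.2.1), and the decision table in Section 11.3 uses those counts. Nor is there any rate from which to estimate how many children would be affected.

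**What to change.** Reword the trigger in Section 6.1.1 so that any hematological DLT under Section 5.5.2 leads to the hold and, on resumption, the next lower level, in parallel with Section 6.2.1. Align footnote 3 of Section 8.1 for later cycles, where counts are weekly; Cycle 1 already has them twice weekly. The footnote's end point, recovery to Grade 3, would also need to change for a DLT that is itself Grade 3.

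The drafting cost is one sentence and one footnote, with no change to sample size, escalation rules or analysis. The clinical cost should be stated openly. There will be additional holds and reductions, of unknown number, in patients already declared dose-limited. A mandatory hold also starts the 14-day clock in Section 6.1.2, so a child whose platelets do not return to 100,000/mm3 in time must come off therapy. That is most plausible under the persistence criterion, in a population without a known curative option (Section 4.1.6).

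If the sponsor wishes to avoid those removals, it can keep the hold and one-level reduction for the Grade 3 events and write in a milder recovery rule for them.
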